#### 11.5 Adverse Event Assessment

#### 11.5.1 Initial Assessment

The investigator must provide the following information:

- Date of onset
- Nature
- Severity
- Duration / date of resolution
- Outcome
- Relationship to investigational device
- Other relevant information

# 11.5.2 Assessment of Severity

The Investigator must determine the severity of the adverse event according to the following definitions:

- **Mild** The adverse event is noticeable to the subject, but does not interfere with routine activity; the symptoms are easily tolerated and transient in nature.
- **Moderate** The adverse event interferes with routine activity but responds to symptomatic therapy or rest; the symptoms are poorly tolerated and sustained.
- **Severe** The adverse event significantly limits the subject's ability to perform routine activities despite symptomatic therapy. The adverse event requires medical or surgical treatment or results in hospitalization.
- **Life-Threatening** The subject is at immediate risk of death.

#### 11.5.3 Device Relatedness

An adverse event is considered device-related when the clinical event has a reasonable time sequence associated with use of the investigational device and is unlikely to be attributed to concurrent disease or other procedures or medications. It is reasonable to believe that the device directly caused or contributed to the adverse event.

The Investigator must provide an assessment of the adverse event according to the following definitions:

- **Definite** The adverse event is clearly related to the investigational device: the event has a temporal relationship to the investigational device, follows a known pattern of response, or is otherwise logically related to the investigational device, and no alternative cause is present.
- **Probable (Likely)** The adverse event is likely related to the investigational device: the event has a temporal relationship to the investigational device, follows a known or suspected pattern of response, or is otherwise logically related to the investigational device, but an alternative cause may be present.
- Possible (Unlikely) The adverse event is unlikely related to the investigational
  device: the event does not follow a clear temporal relationship to the
  investigational device or does not follow a known pattern of response, or is
  otherwise likely to be due to the subject's clinical state or other modes of
  therapy.
- **Not Related** The adverse event is clearly not related to the investigational device: the event has no temporal or other relationship to the administration of the investigational device follows no known or suspected pattern of response, and an alternative cause is present.
- **Unknown** Unable to determine the relationship based on all available information.

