# 5.3 Secondary Endpoints

# **5.3.1** Secondary Safety Endpoints

- Hemoglobin, hematocrit, and free hemoglobin (pre-procedure, immediately postprocedure, and at discharge) will be measured and reported.
- All device and procedure related serious adverse events at 30 days and 6 months post procedure.

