# 11.2 Device Relationship

Determination whether there is a reasonable possibility that a study product or device caused or contributed to an AE is to be determined by the Investigator and recorded on the appropriate CRF form. Determination should be based on assessment of temporal relationships, biologic plausibility, association (or lack of association) with underlying disease and presence (or absence) of a more likely cause.

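### Section 11.5.3 equates Possible with Unlikely and lets one event meet opposing relatedness grades, so a new device effect can be graded unlikely and may be left out of the device-related SAE count

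*Combined protocol and SAP*

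**What the plan says.** Section 11.5.3 gives the investigator five grades: Definite, Probable (Likely), Possible (Unlikely), Not Related and Unknown. The third opens "Possible (Unlikely) The adverse event is unlikely related to the investigational" device. It applies if timing is unclear, if the event fits no known pattern (the wording is "investigational device or does not follow a known pattern of response, or is"), or if the patient's condition or another treatment is the likelier explanation. These are three alternatives, and any one is enough.

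The two higher grades are also built from alternatives. After a temporal relationship, Definite continues "follows a known pattern of response, or is otherwise logically related to the investigational device, and no alternative cause is present". Probable continues "follows a known or suspected pattern of response, or is otherwise logically related to the investigational device, but an alternative cause may be present".

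Two other statements set a standard for relatedness. Section 11.5.3 itself begins "An adverse event is considered device-related when the clinical event has a reasonable time sequence associated with use of the investigational device" and adds that other causes must be unlikely. Section 11.2 asks for a "Determination whether there is a reasonable possibility that a study product or device caused or contributed to an AE", judged on timing, biologic plausibility, underlying disease and more likely causes. Neither mentions a known pattern.

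The endpoint that uses relatedness is in section 5.3.1: "All device and procedure related serious adverse events at 30 days and 6 months post" procedure. Neither that section nor section 8 (Statistics) says which of the five grades count as related.

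**The concern.** Section 11.2 asks whether causation is reasonably possible, but the scale has no grade for an event that is simply possible. The only grade with that name is defined as unlikely.

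The pattern criterion is the more serious part. Section 4.1 describes a first-in-human study, and the preclinical work described in section 1 is two pigs with normal arteries and three cadaver limbs. Patterns specific to this device in patients are therefore few. A serious effect that is new in nature, which section 11.3 treats as a reason for special reporting, is also the kind of event most likely to lack a known pattern. The scale allows such an event to be graded unlikely related for that reason alone.

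Safety is part of the primary objective (section 3). If an event properly fits two opposing grades and the endpoint does not say which grades count, the reported device-related SAE count depends partly on which definition was applied.

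**Working it through.** The plan gives no figure to reproduce: section 8 is descriptive, without hypothesis testing. The check is on the logic of the definitions.

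**1. Coding the grades.** Take five yes/no attributes: T (temporal link), K (known pattern), S (suspected pattern), L (otherwise logically related), A (alternative cause present). That gives 2^5 = 32 combinations. Read literally:

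- Definite: (T or K or L) and not A
- Probable: (T or K or S or L) and A
- Possible (Unlikely): (not T) or (not K). The third alternative, likely due to the subject's condition or other therapy, is left out; it could only add events to this grade.

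**2. Events with no known pattern (K = no).** There are 2^4 = 16 combinations.

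- Possible (Unlikely): all 16 qualify, because K = no is sufficient.
- A = no: Definite needs T or L. Of the 8 combinations of T, S and L, 2 fail (T = L = no, S either way), leaving 6.
- A = yes: Probable needs T, S or L. One of 8 fails, leaving 7.
- So 6 + 7 = 13 of the 16 also meet Definite or Probable.

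**3. No known pattern but a temporal link (K = no, T = yes).** There are 2^3 = 8 combinations. T alone satisfies Definite in the 4 with A = no, and Probable in the 4 with A = yes. So 8 of 8 meet both the low grade and a high one.

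**4. Other readings of the wording.**

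- If Probable is open whether or not an alternative cause is present, step 2 becomes 7 + 7 = 14 of 16. Step 3 stays at 8 of 8.
- If timing is required in addition to a pattern or a logical link, then with K = no and T = yes, Definite needs L (2 of the 4 with A = no) and Probable needs S or L (3 of the 4 with A = yes). The overlap is 2 + 3 = 5 of 8. In the other 3, L = no, so even this reading does not force a logically linked new effect into the low grade.

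These are counts of logical cases, not probabilities.

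**5. The standards side by side.**

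| Text | Known pattern needed? | Alternative cause |
|---|---|---|
| 11.2 | No | Weighed |
| 11.5.3, opening rule | No | Must be unlikely |
| Definite | No, if another alternative is met | Absent |
| Probable | No, if another alternative is met | May be present |
| Possible (Unlikely) | Its absence alone suffices | One sufficient alternative |

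The opening rule and Probable also differ on alternative causes, so the opening rule does not supply the missing mapping from grades to related or unrelated.

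**6. Illustration of size.** Assume 10 treated subjects, a per-subject proportion, and the low grade counted as unrelated. One subject is then 1/10 = 10 percentage points. The exact 95% (Clopper-Pearson) limits are the 0.025 quantile of Beta(x, n − x + 1) and the 0.975 quantile of Beta(x + 1, n − x):

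- x = 0: 0%, interval 0% to 30.8%
- x = 1: 10%, interval 0.3% to 44.5%
- x = 2: 20%, interval 2.5% to 55.6%

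**The case against.** A reader might infer that the scale sends every event without a known pattern to the low grade, and that new device effects therefore drop out of the endpoint. The documents do not support that.

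- **The grade is permitted, not forced.** Definite and Probable can be met through timing or a logical link, and Probable also accepts a suspected pattern. The opening rule of 11.5.3 and section 11.2 would treat a new event with clear timing and no better explanation as device-related.
- **Exclusion is not stated.** No section says Possible (Unlikely) counts as unrelated. Exclusion is a natural reading of the label, but it remains an inference.
- **Known need not mean known for this device.** Section 7.2 calls the risks similar to those of other atherectomy procedures and lists many, so class-level patterns may apply. This narrows the set of affected events without emptying it.
- **There are safeguards.** All adverse events are recorded regardless of relationship (section 11). Serious events go to an independent physician whatever their grade, who decides on UADE status and contribution to the endpoint (section 12.2). The endpoint also takes procedure-related SAEs, and the primary MAE composite (5.1) does not use the scale.

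These points stand, but the safeguards are incomplete. Assigning or regrading relatedness is not among the adjudicator's named tasks, and no mapping tells that physician which grades contribute. Sections 11.4, 11.5.1 and 11.5.3 require a relationship to the device only. No procedure-relatedness scale is defined, so the procedure route cannot be relied on to recover a misgraded event. Recording every event preserves the data but does not define the reported count.

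It is also fair to say that this is a descriptive secondary endpoint in up to 10 subjects. That limits the consequence, but the correction is also small.

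**Conclusion.** The scale is wrong as written. Possible is defined as Unlikely, absence of a known pattern is sufficient for that grade even when timing fits, and on a literal reading all 8 combinations with a temporal link and no known pattern also meet Definite or Probable, with no precedence rule. Under the stricter parse of the higher grades the overlap is still 5 of 8.

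A new device effect can therefore be graded unlikely related and may be left out of the 5.3.1 count. That last step assumes the low grade would be treated as unrelated, which the documents leave open; they are equally silent on Unknown. The size cannot be derived from the documents. The 10-point shift per subject requires the full 10 subjects and a per-subject proportion, which 5.3.1 does not specify. The primary safety endpoint is not affected.

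**What to change.** - In 11.5.3, remove absence of a known pattern as a sufficient criterion for the unlikely grade.
- Separate Possible from Unlikely, and word the grades to be mutually exclusive and consistent with both the reasonable-possibility standard in 11.2 and the section's own opening rule.
- In 5.3.1, state which grades count as device-related, including how Unknown is handled.
- Tabulate SAEs by every grade. Whether Possible and Unknown should count as related is debatable, and a full tabulation lets the reader see the result either way.
- In 12.2, add assignment of device relatedness for each SAE to the independent adjudicator's tasks, and report it beside the investigator's grade.

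The cost is a change to definition and CRF wording and one added task for an adjudicator who already receives the serious events. The device-related SAE count may come out slightly higher. No added visits, tests or subjects are needed.

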# 11.6 Device Deficiency or Malfunction

A Device Deficiency is an inadequacy of a medical device with respect to its identity, quality, durability, reliability, safety or performance (includes malfunctions, use errors, and inadequate

labeling). Sponsor, in cooperation with the CEC, will assess all device deficiencies that could have led to a serious adverse device effect for potential regulatory reporting requirements.

In the event of a suspected malfunction or device deficiency, the investigational device(s) shall be returned to the manufacture for analysis. Instructions for returning the investigational device will be provided by the Sponsor.

# 11.7 Reporting of Death

During the study, all deaths must be reported to the Sponsor within the period outlined in Table 12-1. All deaths also should also be reported on the AE form and End of Study CRF. A copy of the subject's death records, medical records for the events that led to the subject's death, and a death certificate (if available) and an autopsy report (if performed) should be sent to the sponsor. In addition, subject death must be reported to the IRB in accordance with IRB requirements.

#### 12 STUDY ADMINISTRATIV OVERSIGHT

## 12.1 Core laboratory

Independent core laboratories shall be utilized to provide a standardized process and assessment of all angiographic and duplex ultrasound studies. The core laboratories will be responsible for analyzing the angiograms and ultrasound images according to the study eligibility criteria, the study endpoints and this study protocol, for providing feedback to the sites and Sponsor regarding the quality of the tracings and images and for providing a written summary report of all angiograms and duplex ultrasound results to the study Sponsor.

Investigators will enroll subjects into the study based on inclusion and exclusion criteria. Lesion characteristics and measurements will be assessed by investigators using visual estimates; however, the core laboratory will assess by quantitative angiography. Baseline measurements and post-procedure results will be reported by investigator and by core laboratory.

Angiographic and Ultra Sound Core Laboratory Protocols shall be provided to the investigational sites.

# 12.2 Clinical Adverse Event Adjudication

An Independent Adverse Event Adjudicator will be responsible for the adjudication of any events. For this small-scale feasibility study, one physician independent of the study or the sponsor will be responsible for the adjudication of any events that may be considered serious and/or device related by the principal investigator and/or study Sponsor. The physician will be familiar with PTA procedures who is not an investigator in the trial. The adjudication process will include determination of whether the event or device deficiency constitutes a SAE or an UADE, or contributes to the endpoint, and whether the subject should be considered a Procedural Success. All available data (including lab reports, films, discharge reports, etc.) will be available to adjudicate the events.

# 12.3 IRB Approval

The study protocol shall be reviewed and approved by the investigator's IRB prior to subject enrollment. The Sponsor must review any proposed changes to the investigational informed consent prior to implementation.

Prior to shipment of investigational devices, a signed copy of the IRB approval letter identifying the clinical study and investigational site is required to be submitted to the Sponsor. Investigators are responsible for obtaining and maintaining annual renewal of the study by their IRB (or according to renewal schedule imposed by the IRB). Evidence of renewal and continued IRB approval must be provided to the Sponsor accordingly.

#### 12.4 Informed Consent

Informed consent is mandatory and must be obtained from all subjects per local regulations, prior to their participation in the study. Only IRB approved informed consent may be used.

It is the responsibility of the Investigator to ensure written informed consent from each subject, or the legally authorized representative of the subject, is obtained prior to the initiation of any study-related procedures.

Subjects who agree to participate in this study will do so voluntarily. They will be treated on an equal basis with all other patients. Choosing not to participate will not affect their care in any way.

Study personnel fully knowledgeable in the purposes and procedures of the study will approach all prospective study participants. The facilities and settings in which prospective participants will be presented with the opportunity to learn about and consent to participation in the study will provide them sufficient quiet and unhurried time to be informed of the study, to ask questions, and between consent being given and the initiation of study procedures. Study personnel will, after presenting the study to prospective participants, assess the subject's understanding and autonomy by asking the subject to explain the study in his/her own words.

Once that step is completed, consent will be able to be given by the subject's signing the consent form. A copy of the consent form will be given to all consented participants.

Original signed subject consent forms must be retained in the study files by the Investigator, and available for review by the Sponsor and/or regulatory agencies, as applicable.

The informed consent form and any other written information provided to subjects will be revised whenever important new information becomes available, or if there is an amendment to the protocol which necessitates a change to the content of subject information and/or to the consent form. The Investigator will inform the subject of changes in a timely manner, and will ask the subject/patient to confirm his/her continuation in the study by signing a revised consent form.

Any revised informed consent form and other written information provided to subjects must receive IRB, Sponsor, and regulatory agency approval, as applicable.

## 12.5 Records

Each Investigator must maintain the following accurate, complete, and current records relating to the conduct of the study investigation. The final responsibility for maintaining such records remains with the Investigator. These records include, but not limited to:

- All signed agreements;
- IRB/EC approval letter(s);
- Signed ICF;
- Records of AEs, including supporting documents;
- Records of protocol deviations, including supporting documents
- Records showing receipt, use and disposition of all investigational devices, including:
  - o Date, quantity, model and serial numbers of devices received,
  - o Name of person(s) who received, used or disposed of each device,
  - The number of devices returned to the Sponsor and the reason(s) for return;
- All correspondence related to the study;
- Records of each subject's case history, including study-required CRFs, signed ICF, all relevant observations of AEs, the condition of each subject upon entering and during the course of the investigation, relevant medical history, the results of all diagnostic testing, etc.;
- Study personnel visit log;
- Signature authorization and delegation log; and,
- Any other records that applicable regulation requires to be maintained.

The Investigator will maintain all essential trial documents and source documentation that support the data collected on the study subjects in compliance with FDA's GCP guidelines. Documents must be retained until at least 2 years have elapsed since the date the investigation is completed or terminated or the records are no longer required to support a regulatory submission, whichever date is later. These documents will be retained for a longer period of time by agreement with Sponsor or in compliance with other regulatory requirements. The investigator will take measures to ensure that these essential documents are not accidentally damaged or destroyed. If for any reason the investigator withdraws responsibility for maintaining these essential documents, custody must be transferred to an individual who will assume responsibility. The Sponsor must receive written notification of this custodial change.

# 12.6 Reports

Table 12-1 lists those reports that are the investigator's responsibility to deliver to the Sponsor. Each study investigator must follow the EC/IRB reporting requirements for their respective site. If applicable regulations or EC/IRB requirements mandate stricter reporting requirements than those listed, the stricter requirements must be followed.

Table 12-1: Reports Required from Investigators to Sponsor

Type of Report	Prepared by PI for	Notification Time Frame
UADE	Sponsor, EC/IRB	As soon as possible but within 5 working days of knowledge
Death	Sponsor, EC/IRB	Written reports (e.g., via e-mail) within 48 hours
		Within 10 working days of knowledge Per IRB requirement
Device malfunction with clinical sequelae	Sponsor EC/IRB, if required	Within 48 hours via written communication. Return the device to sponsor within 48 hours.
Serious protocol deviations (e.g., ICF not obtained, to protect the life or physical well-being of a subject in an emergency)	Sponsor, EC/IRB	As soon as possible but within 5 working days of knowledge Per IRB requirement
Withdrawal of EC/IRB approval	Sponsor	Within 5 working days of knowledge
Annual progress report	Sponsor, EC/IRB	Annually
Interim report	Sponsor, EC/IRB	Within 14 days of 30-day follow up
Final report	Sponsor, EC/IRB	Within 3 months of study completion or termination

Note: Each IRB/EC may require more stringent reporting requirements that those listed in this table.

# 12.7 Investigator Responsibilities

- Agree to sign and adhere to the Investigator Agreement.
- Obtain approval from the IRB including subsequent protocol amendments and changes to the Informed Consent form and obtaining annual IRB approval and renewal throughout the duration of the study.
- Await IRB approval, as well as, any additional hospital requirements prior to

- requesting written informed consent from any potential study subject or prior to allowing any subject to participate in the study.
- Complete and provide signed copies of all required investigator documentation such as an Investigator Agreement or Disclosure of Financial Interest.
- Agree to participate in Investigator meetings as scheduled by the Sponsor.
- Be willing to perform and be capable of performing treatment procedures as outlined in this protocol.
- Comply with all required elements of this protocol (e.g., perform testing and follow-up as specified, especially during personnel transitions).
- Agree to obtain written Informed Consent before any study specific procedures are performed in accordance with GCP.
- Be willing to change hospital routine if required by protocol (as long as subject safety and well-being is not compromised).
- Control any investigational device(s) stored at their site.
- Be aware of, and comply with, GCP and applicable regulatory requirements.
- Permit monitoring and auditing by the Sponsor, and inspection by the appropriate regulatory authorities.
- Have available an adequate number of qualified staff and adequate facilities to properly conduct the study.
- Ensure study personnel are adequately informed about the protocol, the investigational device and study-related duties and functions.

